All respiratory samples (nasopharyngeal, oropharyngeal, saliva, and sputum samples) will be tested for RSV A and B, PIV serotypes 1-4, and hMPV, by using a commercial RT-PCR kit, which also tests for presence of SARS-CoV-2, Influenza A, Influenza B among others. Study Contributor will be requested to submit validation logs (summarizing the quality check process, results, timing and certificates of analysis for assays performed).

Blood samples:

Acute and convalescent paired blood specimens will be collected for serological testing for RSV A and B, hMPV and PIV 1-4. Blood samples will be centrifuged to separate the serum, which will be stored at -20°C until shipment to the central laboratory in Lyon for testing. Enzyme-Linked Immunosorbent Assay (ELISA) technique will be used to detect and quantify IgG antibody titers. Serology will be considered positive for a recent infection when a 4-fold or greater rise in virus specific IgG antibodies is found between the paired acute and convalescent blood samples.

The laboratory in Lyon will deliver the following variables:

- RSV-A IgG antibody titers baseline
- RSV-A IgG antibody titers convalescence
- RSV-B IgG antibody titers baseline
- RSV-B IgG antibody titers convalescence
- hMPV-A IgG antibody titers baseline
- hMPV-A IgG antibody titers convalescence
- hMPV-B IgG antibody titers baseline
- hMPV-B IgG antibody titers convalescence
- PIV1 IgG antibody titers baseline
- PIV1 IgG antibody titers convalescence
- PIV2 IgG antibody titers baseline
- PIV2 IgG antibody titers convalescence
- PIV3 IgG antibody titers baseline
- PIV3 IgG antibody titers convalescence
- PIV4 IgG antibody titers baseline
- PIV4 IgG antibody titers convalescence

Storage:

To support potential future analyses and ensure the integrity and reproducibility of study findings, multiple biological samples per participant will be collected and aliquots will be stored under controlled conditions for long-term preservation when there is specimen left over.

Variables:

At baseline, information on covariates will be collected from patients in all settings through an electronic Case Report Form (eCRF). Set-up and questions will be based on the eCRF used for the id.DRIVE surveillance project. The following variables will be collected:

- Age
- Sex at birth
- Setting id
- Diagnosis (upper respiratory tract infection or lower respiratory tract infection)
- Admitting diagnosis (Pneumonia, Bronchitis, Bronchiolitis)

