12.5 Variables

12.5.1 Outcome(s)

12.5.1.1 Primary Outcome – Laboratory-confirmed respiratory infection

A laboratory-confirmed respiratory infection is defined as either:

- a positive RT-PCR result from the nasopharyngeal, oropharyngeal, sputum or saliva respiratory sample, and/or
- a positive serology result from paired blood samples (hospitalized patients only).

The outcome of interest for the primary objectives is a laboratory-confirmed infection with one of the viral respiratory pathogens of interest:

- RSV:
 - Subtype A
 - Subtype B
- PIV
 - Serotype 1
 - Serotype 2
 - Serotype 3
 - Serotype 4
- hMPV

The RT-PCR commercial kit will be used on the nasopharyngeal, oropharyngeal, sputum or saliva respiratory samples and will test for additional pathogens as well including Influenza A and B and SARS-CoV-2.

There will be no results for these additional pathogens on the blood samples.

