12.9.3 Data Analysis

12.9.3.1 Detection rates of respiratory pathogens

Positive laboratory results for each respiratory pathogen of interest will be reported by specimen type. This includes nasopharyngeal swabs, saliva, blood, and sputum. Serology is considered positive for recent infection if a fourfold or greater rise in virus-specific IgG antibodies is observed between paired samples. If all samples (respiratory and blood samples) collected in the time frame are negative, the patient is considered as not having any laboratory-confirmed infection.

For each specimen type, the percentage of positive diagnoses will be calculated by dividing the number of patients in whom the pathogen was detected using that specimen (alone or in combination) by the total number of included patients. Detection rates in sputum and blood samples will be calculated by dividing the number of patients in whom the pathogen was detected using that specimen (alone or in combination) by the total number of included patients who provided sputum or blood samples.

Comparative detection rates will be assessed by calculating the percentage increase in positivity when additional specimen types are included, using nasopharyngeal as the reference. This will allow evaluation of the incremental diagnostic value of each specimen type.

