12.12 Limitations of the Research Methods

- The overall sample size and study period are limited, and certain respiratory pathogens or subtypes may occur infrequently, reducing the statistical power to detect associations or draw conclusions for these specific agents.
- RT-PCR offer high specificity. However, a positive RT-PCR result may not indicate causality for a respiratory infection (persistent nucleic acid from previous infection, or asymptomatic carriage).
- This study will be performed in one geographical area which may result in a limited diversity of patients when considering age, race, social economic status, chronic medical conditions and vaccinations status. The generalizability of the study might therefore be limited.
- Although the study period was selected to coincide with the high season of the pathogens of interest in the Valencia region, previous published studies have shown high seasonal variability and the circulation of the pathogens of interest might differ from the expectations.

- Despite good sensitivity and specificity of the selected serology assays, false-negative (e.g., immunodeficiency disorder) and false-positive (e.g., cross-reactivity) test results are possible.
- The second blood sample is scheduled approximately four weeks after hospital admission, when most patients are expected to have returned home. To facilitate follow-up, a nurse will be hired to visit patients at home, or transportation costs will be reimbursed. Nonetheless, some patients may still be lost to follow-up
- Timing of specimen collection: Delays between symptom onset and sample collection may result in declining viral loads, potentially affecting detection rates and diagnostic accuracy.

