13.2.2 Loss to Follow-up

Information from patients included from the PCC and ED ward setting is expected to be complete as all information and samples will be collected within the initial visit. However, in the hospital setting it is possible that patients have been discharged before the CRF has been completed or all samples have been collected. The ICF for the hospital setting will include giving permission to be contacted at home for additional samples and collection of additional data. For patients who provided a first blood sample, a study nurse will go to the patient's home to collect the second blood sample. If the second blood sample could not be collected, the patient will still be included in the analysis as the information from the other specimen types can still be used.

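### Read literally, the blood denominator in section 12.9.3.1 includes patients with only a baseline sample, who can never be serology-positive, so the serology detection rate is understated

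*Protocol*

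**What the plan says.** Section 12.9.3.1 sets separate denominators for the optional specimens. Sputum and blood detections are divided "by the total number of included patients who provided sputum or blood samples". The same section defines the result: "Serology is considered positive for recent infection if a fourfold or greater rise in virus-specific IgG antibodies is observed between paired samples". The Protocol Summary gives the same definition, calling serology positive "when a 4-fold or greater rise in virus specific IgG antibodies is found between the paired acute and convalescent blood samples", and the primary outcome in section 12.5.1.1 also requires paired blood.

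Table 2 in section 12.7 makes the baseline draw optional for inpatients and takes the convalescent draw only where a baseline sample exists. An incomplete pair is therefore a baseline sample alone.

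Loss of the second sample is expected. Section 12.12 describes home visits and reimbursed transport, then adds: "Nonetheless, some patients may still be lost to follow-up". Section 13.2.2 says: "If the second blood sample could not be collected, the patient will still be included in the analysis", and gives the reason: "as the information from the other specimen types can still be used". Section 12.9.1 refers to 150 patients with serology data and calls that analysis exploratory. It does not say whether the 150 are baseline givers or complete pairs.

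**The concern.** The numerator needs two samples and the denominator, as worded, needs one. Every patient whose second sample is missing adds to the denominator and cannot add to the numerator, so the error runs in one direction only.

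The study asks how much is missed when only an NP swab is tested. The primary objective reports results by additional specimen type, and serology is one of those types. A denominator that dilutes the serology rate understates what serology adds. The same gap touches the rule in section 12.9.3.1 for patients without laboratory-confirmed infection: with negative respiratory samples and baseline blood only, serology cannot be determined, yet no undetermined category is provided.

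**Working it through.** **Inputs**
- Denominator: patients who provided blood, n (section 12.9.3.1).
- Numerator: patients with a fourfold rise between paired samples, x (sections 12.9.3.1 and 12.5.1.1).
- Share of blood givers without a convalescent sample, d: not in the protocol. Assumed range 10% to 40%.
- Rate among complete pairs: not in the protocol. Assumed 6.0% for illustration.
- The 150 in section 12.9.1 has no stated derivation, so it cannot be reproduced.

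**Blood detection rate**

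Complete pairs: m = n(1 − d).

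Rate as written: x/n = (x/m) × (m/n) = complete-pair rate × (1 − d).

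This is an identity at any positivity. With an assumed 6.0% among complete pairs:

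| d (assumed) | Rate as written | Relative reduction |
|---|---|---|
| 10% | 6.0% × 0.9 = 5.4% | 10% |
| 20% | 6.0% × 0.8 = 4.8% | 20% |
| 30% | 6.0% × 0.7 = 4.2% | 30% |
| 40% | 6.0% × 0.6 = 3.6% | 40% |

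The two readings of the 150 give the same relative result:
- If 150 are complete pairs with 9 positives (9/150 = 6.0%), then at d = 20% the blood givers number 150/0.8 = 187.5, and 9/187.5 = 4.8%.
- If 150 are baseline givers, then at d = 20% there are 120 pairs and 0.06 × 120 = 7.2 expected positives, and 7.2/150 = 4.8%.

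**Gain over NP**

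Section 12.9.3.1 expresses the gain as a percentage increase over NP. Let g be the patients positive by serology and negative by NP. They can come only from complete pairs.
- NP computed in all blood givers: increase = g / (NP positives in n).
- NP computed in complete pairs: increase = g / (NP positives in m).

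The ratio of the first to the second is (NP positives in m) / (NP positives in n). It equals m/n = 1 − d only if NP positivity is the same in patients with and without the second sample. If NP were computed in all included patients, this factor would not apply.

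**The case against.** The strongest reply is that blood is treated throughout as a paired specimen. The denominator phrase uses the plural, the sentence defining a positive sits in the same section, and section 12.9.1 speaks of patients with available serology data, which a patient with no convalescent titre lacks. On that reading the denominator already means complete pairs. This is a possible reading, but the text does not fix it: the plural follows naturally from a plural subject, Table 2 calls the baseline draw alone a blood sample, and the Data analysis paragraph of the Protocol Summary applies the total patient count to blood, again with no pairing requirement.

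A reader might infer from section 13.2.2 that baseline-only patients are deliberately placed in the blood analysis. The sentence does not support that. It keeps them for their other specimens and is silent on the blood denominator. Nor does the protocol anywhere say that they are counted as serology-negative; that is the arithmetic effect of the literal wording.

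A further reply is that evaluability rules belong in the statistical analysis plan, which is not at hand. That is fair for details such as a line in the attrition diagram. It does not cover the denominator, which the protocol itself fixes.

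Finally, the illustrative shift lies within sampling error: the exact 95% interval for 9/150 is 2.8% to 11.1%, which contains every rate in the table. That limits the practical weight, but imprecision does not justify an avoidable error in a known direction.

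**Conclusion.** The point holds as a defect in a stated rule. Read literally, section 12.9.3.1 gives a serology rate equal to the complete-pair rate times (1 − d), which is 10% to 40% lower in relative terms for an assumed d of 10% to 40%. The factor is exact for the blood rate relative to complete pairs. The 6.0% and the range of d are assumptions.

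It is tempting to go further and say that both the rate and the gain over NP are biased by exactly the proportion lost. The documents do not support that. For the gain, the factor holds only if NP is computed in the same blood givers and loss is unrelated to infection, and section 12.9.3.1 does not say in which patients NP is computed for this comparison. Nor is the factor exact against the true rate if lost patients differ in infection; in-hospital death is a recorded variable in Table 1, so loss unrelated to severity cannot be presumed.

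Severity is moderate. Section 12.9.1 labels the serology analysis exploratory with limited power, and the NP, oropharyngeal and saliva results are unaffected.

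**What to change.** In section 12.9.3.1:
- Define the blood denominator as included patients with both a valid baseline and a valid convalescent titre for the virus in question.
- Compute the NP comparator for the serology gain in those same patients.
- Treat baseline-only patients as serology not evaluable rather than negative, and report their number.

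In section 12.9.1, state whether the 150 are complete pairs. Align the Data analysis paragraph of the Protocol Summary with the revised wording.

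The cost is a few phrases, with no new data or samples. The serology denominator becomes smaller and the interval wider. As a rough guide, with 150 baseline givers, d = 20% and 6.0% among pairs, the Wald half-width goes from 1.96 × √(0.048 × 0.952/150) = 3.4 percentage points as written to 1.96 × √(0.06 × 0.94/120) = 4.2. Restricting to complete pairs does not remove selection from non-random loss, so the report should still describe the patients without a second sample.

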- Chronic conditions/ Comorbidities:
 - o chronic lung disease
 - o chronic cardiovascular disease
 - o hypertension
 - o chronic liver disease
 - o chronic renal disease
 - o type 1 and type 2 diabetes
 - o cancer
 - o immunodeficiency disorders
 - o obesity
 - o neurological disorders
- Immunodeficiency (e.g., on immunosuppressants)
- Long-term care facility residence
- Vaccination status (RSV, Influenza, SARS-CoV-2), including date of last vaccination
- Specimen test results, specimen type, date of sampling
- Symptoms
- Date of symptom-onset

Data sources:

After study enrolment, data will be collected from primary (e.g., laboratory results) and secondary data sources (e.g., vaccination registries, medical files).

Exposure status, brand information and date of vaccination(s) will be ascertained by consulting vaccination registries. Where needed, treating physician or other health care professionals will be contacted to obtain additional information.

Study size:

Target sample size: 1074 (s)ARI patients (450 in hospital; 624 in PCC and ED):

Data analysis:

The rate of respiratory pathogen diagnosis from nasopharyngeal swab alone will be determined by dividing the count of patients in which the respiratory pathogen of interest was detected solely by nasopharyngeal swab by the total patient count involved in this study, thereby yielding detection rates. The same calculation will be performed for the other specimens, oropharyngeal swab, saliva, blood, and sputum, as well as the detection rates when different specimen types are combined. We will determine the increase in detection rates for each specimen added, using nasopharyngeal only as a reference point. Results will also be presented for different subgroups to explain potential heterogeneity. All included patients are required to have at least a nasopharyngeal swab, oropharyngeal swab and a saliva sample. Euler diagrams will be employed to illustrate respiratory pathogen diagnosis per specimen type. The sensitivity for each specimen type and combination thereof will also be computed.

Data management:

Data collected at Study Contributors will be checked for quality and transferred to a dedicated, secured central server hosted by P95. A data management plan (DMP) will be written prior to the start of the data collection. The DMP will describe all functions, processes, responsibilities and specifications for data collection, cleaning, and validation.

Quality control:

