12.3.2 Inclusion Criteria

Individual patients need to fulfil the following inclusion criteria:

- Adults aged 18 years and older

AND

- Meet the (s)ARI case definition

AND

- Willing to have a nasopharyngeal and oropharyngeal swab collected as well as saliva.

AND

- Willing and able to provide informed consent, obtained from the patient or from the patient's Legally Acceptable Representative(s).

Patients are also asked to provide sputum and blood samples for paired serology testing; however, this is optional and consent is provided separately on the ICF.

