12.9.1 Sample Size Considerations

Sample size were calculated assuming paired designs across various scenarios, assuming the addition of one extra specimen per patient and the simplifying assumption that all positives by Method A are also positive by Method B (i.e., the gain equals the proportion A-/B+). These calculations were based on pathogen incidence rates ranging from 1% to 10% and varying levels of improved detection with an additional sample. Across all settings, we expect data from over 1,000 patients with at least two specimens available (approximately 450 inpatients and 624 outpatients).

Under these assumptions, with the planned combined samples ($N \approx 1,074$), we have adequate precision to assess a doubling of detection rates — consistent with the Pfizer North America Multispecimen Study [6] — for pathogens with an incidence between 1% -7% range. For such doublings, the 95% confidence intervals on the gain are expected to be approximately ± 0.6 and ± 1.8 percentage points overall (interval with ≈ 1.2 —3.6 pp), depending on the baseline incidence.

While analyses stratified by settings will be possible, they will have wider confidence intervals due to smaller sample sizes.

The analysis of the 150 patients with available serology data will be exploratory, with limited statistical power, as we expect only a small number of PIV and/or hMPV cases in this subgroup.

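### For sputum and blood the protocol states two incompatible denominators, and neither gives a sound increase over the nasopharyngeal swab

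*Protocol*

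**What the plan says.** Section 11.1 makes the comparison with a single NP swab the primary objective, both overall and for each additional specimen type. Section 12.9.3.1 then fixes the denominators. Its general rule divides the patients positive "using that specimen (alone or in combination) by the total number of included patients". Its exception for sputum and blood divides "by the total number of included patients who provided sputum or blood samples". The comparison follows, by "calculating the percentage increase in positivity when additional specimen types are included, using nasopharyngeal as the reference". That sentence names no denominator of its own.

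The Data analysis paragraph of Section 4 has a different rule. The NP count is divided "by the total patient count involved in this study, thereby yielding detection rates", and then: "The same calculation will be performed for the other specimens, oropharyngeal swab, saliva, blood, and sputum". There is no exception for optional samples.

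On who gives what, Section 4 says: "All included patients are required to have at least a nasopharyngeal swab, oropharyngeal swab and a saliva sample". Sputum and blood are requested as well; "however, this is optional and consent is provided separately on the ICF" (Section 12.3.2). Section 12.7 limits blood to hospitalized patients. Section 12.9.1 bases precision on a paired design and expects 150 patients with serology out of about 1,074.

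**The concern.** What a specimen adds to NP is a within-patient quantity: the patients who are NP-negative and positive on the added specimen. It can be observed only in patients who have both results.

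Under Section 12.9.3.1 as worded, the rate that includes sputum or blood comes from the providers, while the only NP rate available as reference comes from everyone. Providers are a selected group: they consented separately, and for blood they are all inpatients. If their NP positivity differs from that of all patients, the difference is counted as gain or loss from the specimen.

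Under Section 4 the two rates share a denominator, but a patient with no sputum or blood sample is treated as tested and negative. This is a different error, and it pulls the increase towards zero.

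At stake is the part of the primary objective that ranks the added specimens. A specimen with no value could look useful, or a useful one could look weak.

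**Working it through.** **Inputs from the protocol.** 450 inpatients and 624 outpatients, 450 + 624 = 1,074; 150 with serology; a paired design; a doubling as the effect of interest, at incidences of 1% to 7%; a stated 95% half-width on the gain of 0.6 to 1.8 percentage points (all Section 12.9.1).

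**The plan's own figure.** With a paired gain g equal to the baseline rate, the half-width is 1.96 × √(g(1 − g)/N), N = 1,074.
- g = 1%: 1.96 × √(0.01 × 0.99/1,074) = 0.60 points. This matches the lower figure.
- g = 7%: 1.96 × √(0.07 × 0.93/1,074) = 1.53 points, not 1.8. The upper figure appears at g = 10% (1.79 points).

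The mismatch at the upper end is a separate matter and does not bear on this point. What matters here is that the precision refers to a paired gain.

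**Rule 1: Section 12.9.3.1 as worded.** Let p_all be the NP rate in all patients, p_S the NP rate in providers of specimen X, r = p_S/p_all, and G the true relative gain from X among providers. The rate for NP plus X in providers is p_S(1 + G). Against the all-patient reference, the reported increase is

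p_S(1 + G)/p_all − 1 = r(1 + G) − 1.

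With the reference restricted to providers it is p_S(1 + G)/p_S − 1 = G, whatever r is. The protocol gives no rates by subset, so r is an assumption:

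| r | True gain 0% reads | True gain +100% reads |
|---|---|---|
| 0.8 | -20% | +60% |
| 1.0 | 0% | +100% |
| 1.25 | +25% | +150% |
| 1.5 | +50% | +200% |

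A negative increase cannot occur within the same patients, since adding a specimen never removes a positive. The -20% is purely an artefact.

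**Setting mix as one source of r.** Suppose blood providers have the NP rate of inpatients (rates assumed).
- NP 8% in inpatients and 3% in outpatients: p_all = (450 × 0.08 + 624 × 0.03)/1,074 = 54.72/1,074 = 5.09%. Zero gain reads 8/5.09 − 1 = +57%.
- NP 4% and 6%: p_all = (18 + 37.44)/1,074 = 5.16%. Zero gain reads 4/5.16 − 1 = -22.5%.

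**Rule 2: Section 4.** If a share f of patients is sampled and NP rates are equal, added positives arise only in that share, so the reported increase is f × G. For serology f = 150/1,074 = 0.14, and a true doubling reads about +14%. For sputum the expected number of providers is not stated, so f is unknown.

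**Unaffected comparisons.** For the oropharyngeal swab and saliva f = 1 and r = 1 by design, so both rules give G.

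**The case against.** The strongest reply is that the mismatch under Section 12.9.3.1 is inferred. The sentence on the increase does not state its denominator, and Section 12.9.1 assumes a paired design, which points to the same patients on both sides. Section 12.9 also promises an SAP with table shells, where analysis sets are usually spelled out. Part of this stands: the protocol does not positively state that providers are compared with all patients. However, the only NP rate it defines is over everyone, so an SAP that follows the text would inherit the mismatch. The conflict between Sections 4 and 12.9.3.1 is in the protocol itself and needs no inference.

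Section 12.9.1 already calls serology exploratory and of limited power. That lowers the weight for blood but not for sputum. The analysis by setting (Section 12.9.4) removes the inpatient/outpatient mix for blood, but not selection through consent.

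A reader might infer more than the text supports:
- That the whole primary comparison is invalid. It is not: three of the five specimen types are required from every patient.
- That the phrase in Section 12.9.1, "we expect data from over 1,000 patients with at least two specimens available", shows untested patients in the oropharyngeal or saliva denominators. It does not. That calculation models one extra specimen, and three required specimens satisfy a minimum of two.
- That the bias inflates the benefit. The direction depends on r, which the protocol does not give.

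**Conclusion.** The point holds for sputum, blood and any combination that includes them. Sections 4 and 12.9.3.1 give incompatible denominators for the same quantities. Section 12.9.3.1 as worded returns the true gain only if NP positivity is the same in providers and in all patients. Over assumed r from 0.8 to 1.5, a specimen that adds nothing reads anywhere from -20% to +50%, and a doubling from +60% to +200%. Section 4 shrinks the gain by the share sampled, to about +14% for a doubling from serology, assuming equal NP rates. Actual size and direction cannot be known from the protocol. This is a faulty stated rule within the primary objective, not detail left to the SAP, and it can be corrected before analysis without new data.

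**What to change.** In Section 12.9.3.1, state that for sputum, and separately for blood, the NP rate, the rate for NP plus that specimen, and the gain with a paired confidence interval are all calculated in patients with valid results for both, with n shown. For blood, a valid result should mean a complete acute and convalescent pair: a patient with only the first sample cannot show a fourfold rise, and Section 13.2.2 keeps such patients in the analysis. Give the all-patient NP rate as context only.

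A pairwise set does not define the overall comparison, so base the all-patient multi-specimen result on the three required specimens. Show combinations and Euler diagrams that include sputum or blood in the common set of patients who have every specimen displayed. Bring the Data analysis paragraph of Section 4 into line.

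The cost is wording in two sections and a filter in the code. The sputum and serology comparisons will show smaller n and wider intervals. At n = 150 the paired half-width is 1.96 × √(0.01 × 0.99/150) = 1.6 points for a 1% gain and 1.96 × √(0.07 × 0.93/150) = 4.1 points for a 7% gain.
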